Tranexamic acid to Reduce Infection after Gastrointestinal Surgery: the TRIGS Trial

2. Trial registration

Prospectively registered (ClinicalTrials.gov identifier NCT04192435)

3. SAP version

Version: 1.0 Date: 07/11/2025

4. Protocol Version

This document has been written based on information contained in the TRIGS study protocol Version 1.4 dated 30 June 2022.

5. SAP Revisions

This SAP provides additional details and clarifies analysis approaches outlined in the TRIGS study protocol.

6. Names and affiliations

Document prepared by [name], Monash University; and [name], Alfred Hospital

[name]

Signatures:

Signature of senior statistician responsible ([name]):

Date: 13/11/2025

Date: 13/11/2025

Signature of chief investigator ([name]):

3

7. Brief background and rationale

Refer to the protocol for a detailed background to this trial, version 1.4, dated 30 June 2022.

8. Objectives

Research hypothesis:

We hypothesise that among adult patients schedule for elective or semi-elective open or lap-assisted gastrointestinal surgery (oesophageal, gastric, hepatobiliary, pancreatic, colorectal) with one or more risk factors for complications that a bolus of study drug (0.15 ml/kg TxA 15mg/kg before surgical incision, and then infusion at 0.05 ml/kg/h until end of surgery) will reduce the incidence of surgical site infection compared to matched placebo.

Study objective:

Primary objective: To determine whether TxA, compared to matched placebo, decreases the risk of surgical site infection

SAP version: Version: 1.0 Date: 13/11/2025

Section 3: Trial Methods

9. Trial design

International, multicentre, pragmatic, double-blind, placebo-controlled randomised clinical trial.

10. Randomisation

Patients will be randomly assigned using permuted blocks of sizes 6 to 12 from a computer-generated list to either receive IV TxA or placebo on the day of surgery, but after confirmation of scheduling. Random assignment will be done using a computer-generated code, accessed via a web-based service. Group assignment will be stratified by site and diabetes status.

11. Sample size

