In our recently completed RELIEF trial, in which we enrolled near-identical patients to that proposed in this trial, the pooled incidence of SSI was 14% (consistent with global data²) and red cell transfusions were used in 12% of patients. An incidence of SSI of up to 25% has been reported in other at-risk major gastrointestinal surgical cohorts.43, 44 Assuming an incidence of 12%, and using a type I error of 0.05, we require 1,484 per group in order to have 90% power to detect a 30% reduction in SSI to 8.4% (i.e. relative risk 0.7). Were the control group incidence 14%, this sample size provides 94% power to detect a 30% reduction to 9.8%. We plan to enrol 3,300 patients. This will also provide ≥90% power to detect a 30% reduction in blood transfusions.

Assuming 30% of patients are diabetic and an incidence of SSI in non-diabetic patients in the placebo arm of 10%, this sample size provides \approx 70% power to detect a difference in treatment relative risks of 0.55 in non-diabetic patients and 0.94 in diabetic patients on the multiplicative relative risks scale.45

12. Framework

This trial uses a superiority hypothesis testing framework between groups for the primary outcomes. Results will be reported in accordance with the CONSORT 2025 statement.

13. Statistical interim analyses and stopping guidance

Interim analyses will consider the defined study and safety endpoints after enrolment of 50% and 75% of patients, adjusted according to the O'Brien and Fleming method. Results will be made available to the DSMC, consisting of experts in the fields of surgery, infectious diseases and anaesthesia, and an independent statistician (Chair: [name], UK).

Section 4: Statistical Principles

14. Level of statistical significance

All applicable statistical tests will be 2-sided and will be performed using a 5% significance level.

15. Description of any planned adjustment for multiplicity, and if so, including how the type 1 error is to be controlled

No adjustment for multiplicity is planned.

16. Confidence intervals to be reported

All confidence intervals will be two-sided 95% confidence intervals.

17. Analysis Populations and Estimand

Except where stated otherwise, all analyses will be conducted under the principle of modified intention-to-treat, whereby all participants are included in their randomised groups, but only those participants who underwent a surgical incision will be included in the analysis.

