The primary estimand of interest is described in the table below.

Objective: To determine whether TxA, compared to matched placebo, decreases the risk of surgical site infection.

Estimand: Relative risk of incidence of any surgical site infection (superficial, deep, or organ space) among adult patients undergoing elective or semi-elective open or lap-assisted gastrointestinal surgery (oesophageal, gastric, hepatobiliary, pancreatic, colorectal) with one or more risk factors for complications assigned to receive treatment, relative to assignment to receive a matched placebo.

Treatment: 0.15 ml/kg TxA 15mg/kg before surgical incision, and then infusion at 0.05 ml/kg/h until end of surgery

surgery			
ESTIMAND	ANALYSIS		
Target population : adult patients undergoing elective or semi-elective open or lap-assisted gastrointestinal surgery (oesophageal, gastric, hepatobiliary, pancreatic, colorectal) with one or more risk factors	Analysis set: All randomized participants who undergo surgery. Patients assigned to receive TxA through randomization will be the treatment group, patients assigned to receive the placebo the comparator group.		
Variable: SSI (superficial, deep, and organ space), as defined by the US Centers for Disease Control (CDC), 14 up to 30 days after surgery. This includes all five separate categories of SSI, (Superficial Incisional Primary, Superficial Incisional Secondary, Deep Incisional Primary, Deep Incisional Secondary and Organ Space infection).	Outcome measure: Surgical site infection. Trial patients will be seen and have their medical records (and any cultures done) reviewed on a daily basis whilst in hospital, and a formal wound inspection done on Day 3 and day of discharge, plus a 30-day medical record/pathology review done. Any late (>30 postoperative days) notifications of SSI up to 90 days after surgery will be included in the outcome.		
Handling of intercurrent events: - Treatment as randomized not received:	Handling of missing data : Multiple imputation will be applied if >5% of the participants in the analysis		

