These outcomes will be compared between groups using mixed effects linear regression models adjusting for the stratification variable of diabetes, with random effects for the stratifying variable of site.

25. Statistical Methods – adjustment for covariates

Supplementary analyses for the primary outcome and the secondary outcome of any red cell transfusion will adjust for any prognostic variables imbalanced at baseline.

For the primary outcome, variables with apparent imbalance out of the following list will be adjusted for:

- Patient age
- ASA physical status
- Diabetes
- Current smoker
- Oral steroid
- Open surgery

For the outcome of any red cell transfusion, variables with apparent imbalance out of the following list will be adjusted for:

- Patient age
- ASA physical status
- Body mass index (weight/height²)
- Chronic renal disease
- Aspirin
- Preoperative haemoglobin
- Open surgery

26. Statistical Methods – subgroup analyses

Subgroup analyses of the primary outcome and any red cell transfusion will be conducted for the following subgroups:

- i) Age strata (\leq 60 yr; 61–70 yr;71–75 yr;>75 yr);
- ii) Patient sex;
- iii) BMI strata (≤ 18.5 ; $\geq 18.5-25.0$; $\geq 25.0-30.0$; $\geq 30.0-35.0$; ≥ 35.0);
- iv) ASA physical status
- v) Diabetes status (i.e. the stratification variable);
- vi) Country;
- vii) Type of GI surgery;
- viii) Duration of surgery (approximate quartiles)

Models for these analyses will be as described in Section 27 for the primary analysis, including terms for the subgroup indicator and interactions between the subgroup and randomised group. Treatment effects in each subgroup will be reported.

27. Missing data reporting and assumptions/statistical methods to handle missing data

Multiple imputation of outcomes will be undertaken if the proportion of missingness of the primary outcome

is >5%.

Missing baseline characteristics will be imputed using single mean imputation. Baseline characteristics of participants who did and did not provide the primary outcome will be compared, and will be used to inform multiple imputation models. T-tests or Wilcoxon rank-sum tests will be used to compare continuous characteristics (depending on whether these had approximately symmetric distributions or not); chi-squared tests will compare categorical characteristics between participants with and without the primary outcome.

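### Duration of surgery is used as a treatment subgroup although it is known only after study drug is given and may be changed by it, so its quartile effects and interaction can be biased

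*SAP*

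**What the plan says.** SAP Section 26 opens with "Subgroup analyses of the primary outcome and any red cell transfusion will be conducted for the following subgroups", and item viii of the list is "Duration of surgery (approximate quartiles". The subgroup models follow the primary model, "including terms for the subgroup indicator and interactions between the subgroup and randomised group. Treatment effects in each subgroup will be reported".

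The timing comes from other sections. Section 10 assigns patients "to either receive IV TxA or placebo on the day of surgery, but after confirmation of scheduling". Sections 8 and 17 give a bolus "before surgical incision, and then infusion at 0.05 ml/kg/h until end of surgery". Observed duration is therefore known only when study treatment ends.

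Section 26 attaches no caveat to item viii. The SAP's one warning about bias, in Section 28, covers the as-treated and per-protocol analyses only. Section 31, item 3, says the subgroup list is that of protocol Section 7.3, which is not available here.

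**The concern.** Randomisation makes the arms comparable within any subgroup defined before treatment. The other seven subgroups (age, sex, BMI, ASA status, diabetes, country, type of surgery) are of that kind, or essentially so. Duration is not. If TxA shortens some operations, treated patients move into shorter quartiles and bring their underlying risk with them. A treated patient in the second quartile may then be compared with a placebo patient whose operation was easier from the outset.

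An effect on duration is plausible but not documented. The drug is meant to reduce bleeding, and Section 11 considers an effect on transfusion: "This will also provide ≥90% power to detect a 30% reduction in blood transfusions". For the transfusion outcome, bleeding can drive both the length of the operation and the need for blood, so conditioning on duration is hardest to defend there.

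What is at stake is interpretation. A reader of the subgroup results could conclude that TxA works better or worse in operations of a certain length when the pattern comes from selection.

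**Working it through.** **1. The plan's own figure.** Section 11 states "Assuming an incidence of 12%, and using a type I error of 0.05, we require 1,484 per group", for 90% power to detect 12% against 8.4%. With pooled p = 0.102 and a two-sided 5% level:

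n = [1.960·√(2·0.102·0.898) + 1.282·√(0.12·0.88 + 0.084·0.916)]² / 0.036² = 1,483.2, rounded up to 1,484.

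The figure reproduces and is not disputed. Its 12% and RR of 0.70 are used below.

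**2. Model for the bias.** The following inputs are assumptions, not from the SAP. Log duration is normal with SD 0.4. A latent risk U ~ N(0,1) has correlation ρ with log duration. SSI risk is proportional to exp(bU). TxA multiplies risk by 0.70 in every patient and shortens every operation by a fraction δ.

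Put k = bρ and s = ln(1 − δ)/0.4. For a quartile (l, u) of the pooled standardised durations, mean risk is proportional to

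M(l, u) = [Φ(u − k) − Φ(l − k)] / [Φ(u) − Φ(l)] on placebo, and to M(l − s, u − s) on TxA.

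Quartile RR = 0.70 × M(l − s, u − s) / M(l, u). With δ = 0, s = 0 and the RR is exactly 0.70.

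**3. One quartile worked through.** Take δ = 0.10, ρ = 0.7, b = 0.35. Then k = 0.245, s = −0.263, and the lowest pooled cut-point is −0.812.
- Placebo: Φ(−1.057)/Φ(−0.812) = 0.1453/0.2084 = 0.697.
- TxA: Φ(−0.794)/Φ(−0.549) = 0.2137/0.2916 = 0.733.
- RR = 0.70 × 0.733/0.697 = 0.736.
- Treated share of this quartile: 0.2916/(0.2916 + 0.2084) = 58%. In the longest quartile it is 42%.

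**4. Uniform shortening, quartiles 1 to 4, true RR 0.70.**

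| δ | ρ | b | Quartile RRs |
|---|---|---|---|
| 5% | 0.4 | 0.20 | 0.706, 0.707, 0.707, 0.705 |
| 5% | 0.4 | 0.35 | 0.710, 0.712, 0.712, 0.710 |
| 5% | 0.7 | 0.35 | 0.717, 0.722, 0.722, 0.717 |
| 10% | 0.4 | 0.20 | 0.711, 0.714, 0.714, 0.711 |
| 10% | 0.4 | 0.35 | 0.720, 0.725, 0.725, 0.720 |
| 10% | 0.7 | 0.35 | 0.736, 0.745, 0.745, 0.734 |

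The pair ρ = 0.7, b = 0.20 has the same k as ρ = 0.4, b = 0.35, and so the same results. All quartiles lie above the overall RR of 0.70, but they hardly differ from one another: the largest ratio is 0.745/0.734 = 1.015.

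**5. Uneven shortening.** Suppose instead that only operations with U > 1 (16% of patients) are shortened, by 20%. Numerical integration with ρ = 0.7 and b = 0.35 gives 0.72, 0.74, 0.73 and 0.67 when the true RR is 0.70, and 1.03, 1.05, 1.04 and 0.96 when it is 1.00. This is an apparent interaction with no true effect modification.

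**6. Scale.** With 3,300 patients there are 3,300/8 ≈ 412 per arm per quartile. Taking 12% and 8.4% in each quartile:

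SE(log RR) = √[0.88/(412.5·0.12) + 0.916/(412.5·0.084)] = 0.21.

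- A quartile RR of 0.70 has a 95% interval of about 0.46 to 1.06.
- The largest uniform shift, ln(0.745/0.70) = 0.062, is 0.3 of that SE.
- The false contrast in step 5, ln(0.737/0.674) = 0.089, is 0.3 of the SE of a difference between two quartiles (0.21·√2 = 0.30).

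Unlike the SE, the bias does not shrink as the trial grows.

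**The case against.** The SAP reports no operating times and no expected effect of TxA on them. Section 11 anticipates fewer transfusions, not shorter operations. If duration is unchanged, the quartile analysis is valid. This stands, and it is why the point says the effects can be biased. A reader might infer that they are biased, or that the interaction will mislead; the SAP does not support either.

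Uniform shortening produces almost no false interaction. Visible heterogeneity needs shortening concentrated in high-risk operations, and nothing in the SAP indicates that pattern. The shifts are also small beside sampling error. Both points stand and limit the priority.

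The infusion lasts as long as the operation ("then infusion at 0.05 ml/kg/h until end of surgery"), so duration also measures exposure, which is a legitimate reason to be interested in it. That is fair: exposure does not itself create bias. The bias arises only if treatment alters duration.

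The list comes from the protocol, which may qualify the status of this subgroup. Prespecification protects against selective reporting, but it does not make the arms comparable within a quartile. As written, the SAP gives item viii the same standing as the baseline subgroups.

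**Conclusion.** The point holds as a conditional one. Duration of surgery is a post-randomisation variable open to the treatment, and Section 26 analyses it as though it were a baseline feature. Its quartile effects and interaction can be biased for both outcomes.

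The sizes above apply to SSI and rest on the assumed link between duration and risk and on the assumed shortening. No model specific to transfusion was run, so the greater concern there is an argument from mechanism and has no figure attached.

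One of eight subgroup analyses is affected. A reader might infer that the trial's main finding is at risk. It is not: the primary comparison does not condition on duration.

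**What to change.** Take item viii out of the subgroups modelled with an interaction in Section 26. If it is kept because the protocol lists it:
- present the results by duration as descriptive only, with no interaction term or test;
- label duration as measured after randomisation and possibly affected by treatment;
- summarise duration by arm, with median and quartiles, so that readers can see whether it differs.

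Type of GI surgery, already item vii, can carry the question of operative complexity. A subgroup by planned surgical approach is not proposed, because the SAP mentions only open surgery as a covariate (Section 25) and does not say whether a planned approach is recorded.

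Record the change in Section 31. The cost is SAP wording and a small departure from the protocol's subgroup list; no new data are needed.

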patients included in their randomized groups (treatment policy strategy) - Death prior to identification of SSI within the relevant window: if a patient dies prior to the identification of an SSI, their outcome will be "no SSI" ("while alive" strategy)	set have a missing primary outcome. Results of a complete case analysis will also be provided. Supplementary analysis: The analysis of the primary outcome will be repeated in As-treated and Per Protocol analysis sets.		

The relative risk

will

Population-level summary measure: Relative risk | Analysis approach:

of SSI if treated with TxA compared with no TxA.	estimated using a log-binomial model adjusted for the
	stratification variable of diabetes, with random effects
	for the stratifying variable of site.

Section 5: Trial Population

18. Screening Data

Screening data will be collected and a CONSORT flow diagram will be used to summarise this data.

19. Eligibility

Trial inclusion criteria are described in the trial protocol. Reasons for exclusion will be summarised in the CONSORT flow diagram.

20. Recruitment

A CONSORT flow diagram will be used to describe the number of people consented to participate, randomised, allocated to each treatment group, those lost to follow up (including reasons) and analysed.

21. Withdrawal/follow-up

All participants who are enrolled and randomly assigned to a group, and undergo surgery, must be followed for the duration of the study (unless they withdraw consent) even if they are withdrawn from the active phase of the trial. Losses to follow-up (including reasons) will be summarised in the CONSORT flow diagram by treatment group.

22. Baseline descriptive measures

Baseline characteristics will be summarised as appropriate (means and standard deviations for continuous variables that appear to be distributed approximately symmetrically, medians and interquartile ranges for other continuous variables, counts and percentages for categorical variables). Tests of statistical significance will not be undertaken for comparing baseline characteristics of treatment groups; rather the clinical importance of any imbalance will be noted.

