Other infection	Binary outcome: any incidence of urinary tract (UTI) or "other" infection	Binary variable 0 = no other infection; 1 = UTI or other infection	Any clinical documentation of UTI or other infection
Anastomotic leak	Binary outcome: any incidence of anastomotic leak of any grade	Binary variable 0 = no anastomotic leak; 1 = any anastomotic leak	A defect of the intestinal wall at the anastomotic site (including suture and staple lines of neorectal reservoirs) leading to a communication between the intra- an extra luminal compartments. 1. Grade A - anastomotic

SAP version: Version: 1.0 Date: 13/11/2025

Trial: Tranexamic acid to Reduce Infection after Gastrointestinal Surgery: the TRIGS Trial

			leakage results in no change in patients' management 2. Grade B - leakage requires active therapeutic intervention but is manageable without relaparotomy 3. Grade C - anastomotic
			leakage requires re- laparotomy
Peak-C reactive protein (CRP)	Continuous outcome: concentration of CRP	Continuous outcome with lower limit of 0.	Concentration of CRP on postoperative day 3
Days alive and at home up to 30 days after surgery	Number of days at home up to 30 days after surgery	Continuous outcome with range of 0 to 30	Number of days that a patient is alive and at home up to 30 days after surgery.
Postoperative diagnosis of COVID-19	Binary outcome: any diagnosis of COVID-19 in the 30 days after surgery	Binary variable 0 = no diagnosis of COVID-19; 1 = any diagnosis of COVID-19	Any diagnosis of COVID-19 in the 30-day study period
Safety Outcomes			
Thromboembolism	Binary outcome: any incidence of DVT or PE	Binary variable 0 = no no thromboembolism; 1 = thromboembolism	A clinical diagnosis of DVT or PE up to 30 days after surgery
Seizures	Binary outcome: any incidence of seizure	Binary variable 0 = no seizure; 1 = seizure	A seizure up to 30 days after surgery
Cardiovascular events (MI, stroke)	Binary outcome: any incidence of clinical MI or stroke	Binary variable 0 = no cardiovascular event; 1 = cardiovascular event	A clinical diagnosis of myocardial infarction or stroke up to 30 days after surgery
Anaphylactoid reactions	Binary outcome: any incidence of anaphylactoid reaction post-IV study drug delivery	Binary variable 0 = no anaphylactoid reaction; 1 = anaphylactoid reaction	An anaphylactoid reaction following study drug administration

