Missing outcome values will be imputed separately by treatment group. Imputation models will include treatment group, diabetes status, and baseline characteristics that appear to be different between participants who provided complete follow up data and participants who did not. Imputation models for continuous outcomes will also include terms for site. Imputation models for binary outcomes will not include terms for site due to the possibility of perfect prediction in small sites.

Initially, imputation via chained equations will be attempted for outcomes, with separate imputation for each outcome if this imputation fails. Binary outcomes will be imputed using logistic regression models, and continuous outcomes imputed via with predictive mean matching from the 5 nearest neighbours. Imputed datasets will be compared to complete data using density plots for continuous outcomes and plots of proportions for binary outcomes.

28. Additional Analyses

As-treated and per protocol analyses of the primary outcome and any red cell transfusion will also be conducted. As noted in the E9(R1) addendum, these additional analyses may be subject to severe bias and may not correspond to a relevant estimand.

Data collected prior to the trial re-start (the "contamination dataset") will also be considered. A table summarizing the baseline characteristics of patients by randomised treatment group will be presented. The primary outcome, red cell transfusion outcomes, and healthcare associated infections will be analysed as described above in this dataset.

29. Harms

Safety outcomes and adverse events will be reported by treatment group.

30. Statistical Software and code

Stata v19 or later will be used (StataCorp. Stata Statistical Software: Release 19. College Station, TX: StataCorp LLC); or R v 4.4.1 or later. Any user-written R packages used will be referenced.

The following code will be applied for the analysis of primary and secondary outcomes:

Primary outcome and binary secondary outcomes:

```
xi: gllamm outcome i.TreatmentGroup i.diabetes, i(site) fam(binomial)
link(log)
```

Primary outcome and binary secondary outcome backup code:

```
binreg outcome i.TreatmentGroup i.diabetes, rr cluster(site)
```

DAH30:

```
qreg2 outcome i.TreatmentGroup i.diabetes, cluster(site)
qreg2 outcome i.TreatmentGroup i.diabetes, cluster(site)
```

Continuous outcomes:

mixed outcome i.TreatmentGroup i.diabetes || site: , reml

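### One 5% switch, set by missing SSI, decides whether every outcome is imputed; day-3 CRP can be substantially missing and still be analysed in measured patients only

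*SAP*

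**What the plan says.** Section 27 opens with the rule: "Multiple imputation of outcomes will be undertaken if the proportion of missingness of the primary outcome" is above 5%. The estimand table in Section 17 has the same trigger for the primary analysis ("Multiple imputation will be applied if >5% of the participants in the analysis" "set have a missing primary outcome. Results of a complete case analysis will also be provided").

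The rest of Section 27 shows that imputation is meant to reach secondary outcomes too: "imputation via chained equations will be attempted for outcomes, with separate imputation for each outcome if this imputation fails". Binary outcomes use logistic regression, with "continuous outcomes imputed via with predictive mean matching from the 5 nearest neighbours". No secondary outcome has its own threshold or any other missing-data method.

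Auxiliary variables follow the same outcome: "Baseline characteristics of participants who did and did not provide the primary outcome will be compared, and will be used to inform multiple imputation models". Section 22 describes the same comparison.

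Section 23 defines the CRP outcome as "Concentration of CRP on postoperative day 3". Section 24 says of CRP and red cell volume: "These outcomes will be compared between groups using mixed effects linear regression models". The model adjusts for diabetes and has a random effect for site. The Stata line in Section 30 matches this, with one row per patient.

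**The concern.** The switch watches an outcome that is easy to recover and ignores one that is easy to lose. Under Sections 17 and 23, SSI comes from daily review in hospital, wound inspections, and a review of records and pathology at 30 days, with late notifications accepted to day 90. A patient who dies before an SSI is identified is scored as free of infection, so death does not make SSI missing. CRP exists only if blood is taken and tested on one particular day. Discharge before day 3, death before day 3 or no test that day loses CRP and leaves SSI known.

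At stake is the CRP comparison. Being in hospital and tested on day 3 is a state reached after randomisation. If treatment shifts it, and the patients measured differ in CRP from those not measured, the comparison of measured patients no longer estimates the effect in all randomised patients who had surgery. The method already planned for continuous outcomes would then stay switched off, because SSI happened to be nearly complete.

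The rule also misfires the other way: once SSI missingness passes 5%, secondary outcomes that are almost complete are imputed as well.

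**Working it through.** The plan derives no figure on this point, so the rule is applied first and the possible bias is then illustrated.

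**Step 1: when the switch operates.** Inputs: 3,300 patients (Section 11, taken here as the analysis set) and the 5% threshold (Sections 17 and 27).

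- 0.05 × 3,300 = 165, so imputation starts at 166 or more missing SSI outcomes.
- At 1%, 3% or exactly 5% missing SSI it is off, whatever the CRP missingness.
- CRP missingness is not given. If it were 10%, 20%, 30% or 40% (assumed), then 330, 660, 990 or 1,320 patients would have no value, leaving 2,970, 2,640, 2,310 or 1,980.

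**Step 2: what the CRP model does with missing values.** It has one outcome value per patient. A linear mixed model uses partly observed patients only when they contribute other outcome values, and here there are none. A patient without CRP drops out. The comparison is therefore complete-case in effect, adjusted for diabetes and site.

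**Step 3: possible bias, under assumed values.** None of these inputs is in the SAP.

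- Baseline severity S has a standard normal distribution. T = 1 for TxA and 0 for placebo.
- CRP = constant + 50 × S − 10 × T + residual (SD 50), in mg/L. The true difference is −10.
- logit P(measured) = 1.3 + b × S + g × T. With b > 0, sicker patients are measured more often; g sets the gap between arms.
- Diabetes and site are left out.

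Complete-case difference = −10 + 50 × [mean S of measured TxA patients − mean S of measured placebo patients]. Evaluated by numerical integration:

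| b, g | Missing, placebo | Missing, TxA | Gap (points) | Mean S, placebo / TxA | Complete-case difference |
|---|---|---|---|---|---|
| 1.0, 0 | 25.2% | 25.2% | 0 | 0.215 / 0.215 | −10.0 |
| 1.0, −0.1 | 25.2% | 26.9% | 1.6 | 0.215 / 0.228 | −9.4 |
| 0.5, −0.3 | 22.5% | 27.9% | 5.4 | 0.108 / 0.133 | −8.7 |
| 1.0, −0.3 | 25.2% | 30.3% | 5.1 | 0.215 / 0.255 | −8.0 |
| 1.0, −0.5 | 25.2% | 34.0% | 8.7 | 0.215 / 0.284 | −6.5 |

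Example, last row: −10 + 50 × (0.2843 − 0.2151) = −10 + 3.46 = −6.5.

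**Step 4: against sampling error.** With 1,650 per arm the standard error of the complete-case difference is about 2.8 mg/L in each row. The biases in the last three rows (1.3, 2.0 and 3.5) are about 0.4, 0.7 and 1.2 standard errors.

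**Step 5: what imputation can do.** Simulated imputation by arm on S returned −10.0 in the last three scenarios. That is built in, because missingness there depends only on arm and the same observed S. In a separate run where measurement depended on CRP itself (25% and 28% missing), complete-case gave −8.7 and imputation on the baseline score −9.3. That removes 0.6 of a bias of 1.3, less than half.

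**The case against.** The strongest reply is that the missing CRP is supposed, not shown. The SAP gives no expected missingness, length of stay or day-3 sampling practice. A formal wound inspection on Day 3 is planned, and any blood schedule may sit in the protocol. This stands. A reader might infer that CRP will be heavily missing, but the SAP's definitions show only that it can be while SSI is nearly complete.

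A reader might also infer that heavy missingness biases the comparison by itself, or that a 13% to 35% attenuation is to be expected. In this model it is not so: with 25% missing in both arms there is no bias, even though sicker patients are measured more often. The larger figures need arm gaps of 5 to 9 points, and nothing in the SAP says TxA would produce them.

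Nor would imputation necessarily restore the true difference; Step 5 shows it may do less than half the work. For patients discharged before day 3 there may be few measured donors with similar stays.

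Three smaller points also stand. A single switch on the primary outcome is a simple prespecified rule and contradicts nothing else in the SAP. The SAP never says CRP will be analysed complete-case; that follows from the model and the lack of any alternative. And the imputation would not go unused in all cases, only when SSI missingness is 5% or less.

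None of this answers the structural point that missing SSI says little about missing CRP.

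**Conclusion.** The point holds as a weakness in a stated rule. SSI missingness alone decides whether any outcome is imputed and which auxiliary variables are used. Followed as written, with SSI missing in at most 165 of 3,300 patients, the rule leaves CRP unimputed however much of it is absent.

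The size is unknown from the SAP. Under the assumed model it runs from no bias at equal missingness, through about 0.6 mg/L on a true −10 at a 1.6-point gap, to 1.3 to 3.5 mg/L at gaps of 5 to 9 points. These figures rest on the assumed severity effect, residual SD and selection model. Imputation removes the bias only if CRP is missing at random given the variables in the imputation model.

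The change is worth making because it is cheap and avoids a choice after the fact if CRP proves poorly recorded. A reader might infer that the trial's main result is at risk. It is not: CRP is a secondary outcome, and the SSI analysis and its estimand are untouched.

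**What to change.** Replace the opening rule of Section 27 with wording such as: *Multiple imputation will be undertaken for any outcome whose own missingness in the analysis set exceeds 5%, with auxiliary variables chosen by comparing baseline characteristics of patients with and without that outcome; a complete-case analysis will also be reported.*

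Both halves are needed. Changing the trigger alone would leave the CRP imputation model built around predictors of missing SSI.

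Two details to settle at the same time:

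- Patients who die before day 3 have no day-3 CRP to recover. State separately how they are handled for this outcome; do not impute them.
- Imputation models for continuous outcomes already include site terms. Do not add Country to them, since site determines it.

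The cost is a few sentences in the SAP and one more imputation run with methods already planned. The downside is reliance on missing at random for CRP, which is why the complete-case result should stand beside the imputed one.
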